### 5.3 LIFESTYLE CONSIDERATIONS

To be eligible for this study patient must comply with the following:

- Patients should not have LipiFlow® or other lid-heating therapy, meibomian gland probing, or therapeutic gland expression in either eye within 6 months of the screening visit or during the study.
- Patients must have discontinued (2 weeks before screening) and be willing to remain off other MGD treatments (e.g., at-home warm compress therapy, eyelid hygiene, eyelid massage, and manual lid expression) during the study.
- Patients should not have punctal plugs or plan to have punctal plugs inserted during the study.
- Patients must have discontinued (1 month before screening) and be willing to remain off antihistamines or isotretinoin during the study.
- Patients must have discontinued (3 months before screening) and be willing to remain off Anti-inflammatory treatments for DED (e.g., cyclosporine ophthalmic emulsion [Restasis® or Ikervis®] or lifitegrast ophthalmic solution [Xiidra®]).
- Patients should avoid the use of medicated shampoos containing selenium (e.g., Selsun Blue, Exsel, Selsum, and Seleen) following the screening visit.
- Patients must have discontinued (2 weeks before screening) and be willing to remain off all other prescription medications used for dry eye or MGD (e.g., antibiotics, corticosteroids, and non-steroidal anti-inflammatory drugs) during the study.

- Patients must have discontinued all other topical ophthalmic preparations (including artificial tear substitutes) other than the study drops 72 hours prior to the screening visit. If artificial tear substitutes were used within 72 hours of the screening visit the visit should be rescheduled.
- Patients must avoid periocular application of makeup during the study

Patients should be instructed to strictly follow the visit schedule and to report any changes in condition to the investigative site personnel.

The patients should be instructed to maintain a stable dose of any concomitant medication used chronically, or any new medication initiated during the study if possible. Patients should be instructed to communicate any changes to their medication at their next study visit. Patients should also be reminded to contact the study site if they experience difficulties during their study participation.

Patients should refrain from using any ophthalmic preparations other than study treatment in order to obtain an accurate assessment of their signs and symptoms. Patients should be instructed to communicate any changes to their ophthalmic preparations other than study treatment at their next study visit.

#### 5.4 SCREEN FAILURES

Screen failures are defined as participants who consent to participate in the clinical trial but are not subsequently randomly assigned to the study intervention or entered in the study. A minimal set of screen failure information is required to ensure transparent reporting of screen failure participants, to meet the Consolidated Standards of Reporting Trials (CONSORT) publishing

requirements and to respond to queries from regulatory authorities. Minimal information includes demography, screen failure details, eligibility criteria, and any serious adverse event (SAE).

Individuals who do not meet the criteria for participation in this trial (screen failure) because of normal variability in safety or efficacy measures (e.g., minimally important clinical difference for OSDI) may be rescreened one additional time. Rescreened participants should be assigned a new screening number and the original number should not be reused.

## 5.5 STRATEGIES FOR RECRUITMENT AND RETENTION

The total number of randomized patients for the study will be up to approximately 30. Approximately 15 patients should have a baseline MGS score of < 6 and approximately 15 patients should have a baseline MGS score  $\geq 6$  and  $\leq 12$ . Based upon data from ongoing study AZ201801 and the simplified inclusion/exclusion criteria for this study a screen failure rate of ~40% is expected. Thus, ~42 patients will need to be screened to achieve ~30 patients randomized to treatment.

Individual study sites may choose to advertise the study in order to facilitate patient recruitment. All advertisements will be approved by the sponsor Azura Ophthalmics, submitted to their IEC, and approved by the IEC before they are used by the site.

## 6 STUDY INTERVENTION

### 6.1 STUDY INTERVENTION(S) ADMINISTRATION

#### 6.1.1 STUDY TREATMENT(S)/ FORMULATION(S)/ MEDICAL DEVICE COMPOSITION OR DESIGN

AZR-MD-001 Ophthalmic Ointment contains the drug product, AZR-MD-001 (0.5%), and suitable excipient. The only excipient in the formulation is Petrolatum white. The AZR-MD-001 vehicle and product labelled "Vaseline" for use at the baseline visit contain only Petrolatum white. The formulations will be supplied in identical unit dose containers (see Table 6.1.1–1).

Table 6.1.1–1 Investigational Product and Packaging / Labelling Characteristics

Product name:	AZR-MD-001 (Selenium disulfide API in ointment/semi-solid Petrolatum white)	Vaseline	Vehicle
Formulation description:	AZR-MD-001 is an orange opaque dispersion ointment with an odor faintly of hydrogen sulfide	Ointment will match AZR-MD-001's texture	Ointment will match AZR-MD-001's texture
Dosage form:	Ophthalmic ointment/semi-solid drug	Ophthalmic ointment/semi-solid drug	Ophthalmic ointment/semi-solid drug
Unit dose strength(s)/Dosage level(s):	0.5%/5mg	Placebo Petrolatum, white	Placebo Petrolatum, white
Route of Administration	Topical	Topical	Topical
Dosing instructions:	Store between 2 – 8°C until opened. Refrigerate. Do not freeze. Discard 4 weeks (30 days) after opening. Protect from light	Store between 2 – 8°C until opened. Refrigerate. Do not freeze. Discard 4 weeks (30 days) after opening. Protect from light	Store between 2 – 8°C until opened. Refrigerate. Do not freeze. Discard 4 weeks (30 days) after opening. Protect from light
Physical description:	An orange opaque ointment packaged in a multi-use tube	A white opaque ointment packaged in a multi-use tube	A white opaque ointment packaged in a multi-use tube
Device:	Multi -use white tube with cap	Multi -use white tube with cap	Multi -use white tube with cap
Method for individualizing dosage:	Each container/tube is placed in an individual package and appropriately labelled.	Each container/tube is placed in an individual package and appropriately labelled.	Each container/tube is placed in an individual package and appropriately labelled.

API = Active pharmaceutical ingredient

### 6.1.2 SELECTION OF DOSES IN THE STUDY

Azura Ophthalmics is further evaluating the safety, tolerability and effectiveness of AZR-MD-001

ointment/semi-solid drug, surfactant free, at an effective concentration of 0.5% based upon positive results from clinical studies MGSS1 and AZ201801 (see the Investigators' Brochure for more detail) that demonstrated the safe and effective treatment of MGD with selenium sulfide exposures up to 1.0% twice-weekly, pre-clinical safety data with exaggerated dosing up to 2.5% with the clinical formulation and concentrations up to 2.5% fulfil the criteria for a low risk Schedule 2 (Pharmacy medicine) classification as specified in the Australian Poisons Standard October 2017 (Standard for the Uniform Scheduling of Medicines and Poisons (SUSMP), No. 18) (see Table 6.1.2-1).

Table 6.1.2-1: Australian Poisons Standard for Selenium

Australian Poisons Standard Dated 26th September 2017			
Schedule	Description	Topical	Oral
1	Schedule is intentionally blank.		
2	Pharmacy Medicine -Safe use may require advice from a pharmacist or licensed person.	For human topical use of 3.5% or less	For human oral use with a recommended dose of 150 micrograms or less
3	Pharmacist Only Medicine -Safe use requires advice from a pharmacist without a prescription.		
4	Prescription Only Medicine -Use should be ordered by persons permitted by State or Territory legislation to prescribe and should be available from a pharmacist on prescription.		For human oral use with a recommended dose of 300 micrograms or more
6	Poison -Substances with a moderate potential for causing harm, the extent of which can be handled through distinctive packaging and strong safety labeling.	In this schedule if it occurs with an "arsenic" (i.e., selenium arsenide)	

Azura Ophthalmics believes that the use of AZR-MD-001 ointment/semi-solid drug with selenium disulfide at a concentration of 0.5% is likely to safely and effectively treat MGD.

### 6.1.3 DOSING AND ADMINISTRATION

Patients (or a caregiver) will dispense a dose of approximately 3.5mm (0.14inch, 4mg) using a dosing aid supplied by Azura Ophthalmics. Patients will then use their washed index finger to apply the drug to the tarsus of the lower lid of both eyes in the evening just before bedtime. They will be instructed to press the ointment strip against their index finger to leave a thin and uniform ointment layer over the finger. The patient will then apply the thin drug film and blink several times to transfer a portion of the drug from the lower eyelid to the upper eyelid (see the Dosing Instruction Sheet for more detail).

Multi-dose tubes of the masked study medication are each to be used for only 30 days to both eyes. The patient should be instructed to place the used tube in the used tube bag after use and should return used and unused tubes at the next study visit.

## 6.2 PREPARATION/HANDLING/STORAGE/ACCOUNTABILITY

### 6.2.1 ACQUISITION AND ACCOUNTABILITY

Subjects will be instructed on proper instillation and storage of study drug at the end of the baseline, day 14, month 1, and month 1.5 visits, will be given written instructions and may also

watch an instructional video. The used and unused study drug tubes will be collected at each visit from day 14 up to and including month 3 to assess dosing and symptom assessment compliance. Dosing compliance will be based off of the used and unused tube count.

#### 6.2.2 FORMULATION, APPEARANCE, PACKAGING, AND LABELING

The study packaging will be performed by PCI Pharma Services. All packaging and labeling operations will be performed according to Good Manufacturing Practice for Medicinal Products and the relevant regulatory requirements.

Details of packaging and labeling are in final study documentation provided by PCI Pharma Services.

#### 6.2.3 PRODUCT STORAGE AND STABILITY

The study medication must be stored in a secure area accessible only to the investigator and his/her designees. The study medication will be administered only to patients entered into the clinical study, in accordance with the conditions specified in this protocol.

The study medication is to only be prescribed by the principal investigator or his/her named sub-investigator(s) or a pharmacist, and is to only be used in accordance with this protocol. The study medication must only be distributed to patients properly qualified under this protocol to receive study medication.

The investigator must keep an accurate accounting of the study medication received from the supplier. This includes the amount of study medication dispensed to patients, amount of study medication returned to the investigator by the patients, and the amount returned or disposed upon the completion of the study. A detailed inventory must be completed for the study medication.

All study medication will be returned to the sponsor or their designee or destroyed at the study site. The return or disposal of study medication will be specified in writing. AZR-MD-001 is to be refrigerated between 2 – 8°C until opened and protected from light. Maintenance of a temperature log (manual or automated) is required at the clinical sites.

#### 6.2.4 PREPARATION

Patients should let the study tube equilibrate at room temperature below 25°C for up to 15 minutes before dosing. Patients will use the study medication directly from the dose container in accordance with the protocol and should return the dose container to refrigeration between 2 – 8°C following successful dosing. For the next day of dosing, this process should be repeated.

This in use pattern should continue for 30 days at which time the dose container should be used for a final day of dosing and then discarded.

### 6.3 MEASURES TO MINIMIZE BIAS: RANDOMIZATION AND BLINDING

Patients (or a caregiver) will apply approximately 3.5mm (0.14inch, 4mg) using a dosing aid supplied by Azura Ophthalmics. Patients will use their washed index finger to apply the drug to the tarsus of the lower lid of both eyes in the evening just before bedtime. The patient will then blink several times to transfer a portion of the drug from the lower eyelid to the upper eyelid.

To minimize the risk for noncompliance with the dosing instructions patients enrolled into the clinical study will be given dosing instructions and will have access to instructional dosing videos. Additionally, site personnel will observe patients applying ointment from a tube labelled "Vaseline" at the baseline visit, and will have access to instructional dosing videos.

Only patients demonstrating an understanding with the provided dosing instructions can be enrolled into the clinical study.

Following the qualification period, the patient, staff members performing all safety and efficacy assessments, site personnel (with the exception of designated personnel who are responsible for drug accountability) and the sponsor study team will be masked to the treatment assignment for the 3 month treatment period. All study medication will be provided in identical tubes and cartons to maintain masking of the study. Due to the difference in color between the active and control treatments, which are in opaque tubes, designated personnel who are responsible for drug accountability will not perform any safety or efficacy assessments and will not discuss assigned treatment(s) with staff members who are performing safety or efficacy assessments.

To obtain a screening number at the screening visit the site will access an electronic data capture (EDC) system and complete the appropriate electronic Case Report Form (eCRF). The numbers will be assigned sequentially by site.

The automated IWRS system will provide the site with the specific medication kit number(s) to use for each qualified patient at the baseline visit. At the baseline/randomization visit, patients meeting all inclusion/exclusion criteria, will be placed in one of the strata. A randomization number will be assigned to each patient corresponding to the treatment arm they are assigned to. The numbers will be assigned sequentially in order of enrollment within the patient's stratum. The IWRS system will report a medication kit number to use for each patient corresponding to the randomization number.

The site will dispense the study medication kit assigned by the IWRS system. Sites will log onto the IWRS system at all subsequent study visits to obtain medication kit number for dispensing study medication. Sites will receive an IWRS confirmation notice for each transaction. All notifications are to be maintained with the study source documents.

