**Figure 1 Study Flow – Multicenter, investigator-masked, vehicle-controlled, randomized, parallel group study**

### 1.3 SCHEDULE OF ACTIVITIES (SOA) COHORT 1 AND EXPANSION COHORT

**Table 1 Schedule of Visits and Procedures**

Study Period	Qualification Period		Investigator-Masked Period			
	Screening a (Day -14)	Baseline Day 0 Randomization	Day 14	Month 1	Month 1.5	Month 3 (Exit)
Visit Window	$\pm 2$ Days	N/A	$\pm 2$ Days	$\pm 7$ Days	$\pm 7$ Days	$\pm 7$ Days
Informed consent/authorization	X					
Contact IVRS/IWRS for patient number assignment (screening number)	X					
Demographics (including height and weight)	X					
Inclusion/exclusion criteria	X	X				
Medical and ophthalmic history	X	X				
Medication history	X					
Washout medications	X					
Vital signs (pulse rate, blood pressure) f	X	X		X		X
Pregnancy test (urine) for female patients b, f	X					X
OSDI f	X	X	X	X	X	X
SPEED f	X	X	X	X	X	X
Patient Ocular Symptoms (VAS) f	X	X	X	X	X	X
Best-corrected visual acuity (BCVA) f	X c	X	X	X	X	X
Slit-lamp biomicroscopy (includes eyelid margin erythema/telangiectasias and do not touch the lids) f	X	X	X	X	X	X
Tear Break Up Time (TBUT) e, f	X	X	X	X	X	X
Sodium fluorescein corneal staining, Oxford scale f	X	X	X	X	X	X
Lissamine green conjunctival staining, Oxford scale f	X	X	X	X	X	X

Study Period	Qualification Period		Double-Masked Period			
	Screening a (Day -14)	Baseline Day 0 Randomization	Day 14	Month 1	Month 1.5	Month 3 (Exit)
Visit Window	$\pm 2$ Days	N/A	$\pm 2$ Days	$\pm 7$ Days	$\pm 7$ Days	$\pm 7$ Days
Meibomian gland evaluation (MGE) e, f	X	X	X	X	X	X
Schirmer without anesthesia f	X	X		X		X
Intraocular pressure (IOP) f	X					X
Ophthalmoscopy exam d	X					X
Meibography f	X					X
Study medication Tolerability/Comfort Questionnaire f		X g	X	X	X	X
Adverse events/medications/procedures f	X	X	X	X	X	X h
Discontinue concomitant medication(s) impacting inclusion/exclusion	X					
Contact IVRS/IWRS for patient randomization number		X				
Medication dispensing/return		X	X	X	X	X
Physician Observation of Drug Application Methods		X				

BCVA = Best Corrected Visual Acuity; OSDI = Ocular Surface Disease Index; SPEED = Standard Patient Evaluation of Eye Dryness; TBUT = tear break up time;

VAS = Visual Analogue Scale; PM = Evening

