## **4 STUDY DESIGN**

### **4.1 OVERALL DESIGN**

This is a multicenter, investigator-masked, vehicle-controlled, randomized, parallel group study comparing AZR-MD-001 (0.5%) ointment/semi-solid drug and AZR-MD-001 vehicle dosed twice-weekly in the evening.

Patients with MGD will be randomly assigned in a 1:1 ratio to receive either a single concentration of AZR-MD-001 ointment/semi-solid drug (i.e., 0.5%) or AZR-MD-001 vehicle.

For all dose groups a screening visit will be followed by a baseline visit 14 days later (qualification period). At the end of the qualification period patients who still exhibit signs of MGD and who can comply with dosing instructions will be enrolled into a 3-month treatment period. The study flow is shown in Figure 1.

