2 SUMMARY

TITLE	A Multicenter, Vehicle-controlled, Randomized Study to Evaluate the Safety, Tolerability and Pharmacodynamics of AZR-MD-001 in Patients with Meibomian Gland Dysfunction (MGD)
PREFACE	
This Statistical Analysis Plan (SAP) describes the planned analysis and reporting for Azura protocol AZ202001 (Multicenter, Vehicle-controlled, Randomized Study to Evaluate the Safety, Tolerability and Pharmacodynamics of AZR-MD-001 (Selenium disulfide Agonist) in Patients with Meibomian Gland Dysfunction (MGD). This study is being completed to assess the safety, tolerability, and pharmacodynamics of AZR-MD-001 in patients with meibomian gland dysfunction (MGD).
 
The following documents were reviewed in preparation of this SAP:
 
 • Clinical Research Protocol AZ202001 issued 12MAR2020 • Case report forms (CRFs) issued 25JUN2020 for AZ202001
PURPOSE	The purpose of this SAP is to outline the planned analyses in support of the Clinical Study Report (CSR) for protocol AZ202001. Exploratory analyses not necessarily identified in this SAP may be performed to support the clinical development program. Any post-hoc, or unplanned, analyses not identified in this SAP will be clearly identified in the respective CSR.
STUDY OBJECTIVES	To evaluate the safety, tolerability, and pharmacodynamics of AZR-MD-001 ointment/semi-solid drug applied to the lower lid twice weekly for up to 3 months compared to its vehicle in patients with meibomian gland dysfunction (MGD).
STUDY DESIGN	Multicenter, investigator-masked, vehicle-controlled, randomized, parallel group study comparing AZR-MD-001 (0.5%) ointment/semi-solid drug and AZR-MD-001 vehicle dosed twice-weekly in the evening.
ENDPOINTS	
The study's primary efficacy sign for MGD is change from baseline to month 3 in meibum gland secretion score (MGS) (0 to 45 scale). The study's primary efficacy symptom for MGD is change from baseline to month 3 in total OSDI.
 
Other Efficacy Measures:
 
 • Change from Baseline to day 14, month 1 and month 1.5 in MGS (0 to 45 scale) • MGS score (0 to 45 scale) at each visit • Proportion of patients with an MGS score > 12 at each visit • Change from Baseline to day 14, month 1, month 1.5 and month 3 in the number of Meibomian Glands Yielding Liquid Secretion (MGYLS)

	TEMPLATE		
	DOCUMENT #:		TMP-191
	REVISION:		2.0
STATISTICAL ANALYSIS PLAN TEMPLATE	CC #:	836	PAGE 9 OF 25

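### Protocol 6.3 and one Table 1 heading present patients as masked in a study otherwise labelled investigator-masked; with an orange active and a white vehicle, patient masking is not assured for the patient-rated primary endpoint, Total OSDI

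*Protocol*

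**What the plan says.** **Who is masked.** Protocol 6.3 opens its masking sentence with "Following the qualification period, the patient, staff members performing all safety and efficacy assessments, site personnel". After excepting the drug-accountability staff, it ends "and the sponsor study team will be masked to the treatment assignment for the 3 month treatment period". Table 1 (Protocol 1.3) is split in two. The first part heads the treatment visits "Investigator-Masked Period" and the second part heads the same visits "Double-Masked Period". Protocol 4.1 says "This is a multicenter, investigator-masked, vehicle-controlled, randomized, parallel group study". Protocol 1.2, the Figure 1 title and SAP section 2 carry the same label (SAP: "Multicenter, investigator-masked, vehicle-controlled, randomized, parallel group study comparing AZR-MD-001 (0.5"). SAP section 13, which lists changes from the protocol, does not mention masking.

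**What the products look like.** Table 6.1.1–1 says "AZR-MD-001 is an orange opaque dispersion ointment with an odor faintly of hydrogen sulfide". It describes the vehicle and the practice product as white and states a match on texture; it states none on colour or odour. Section 6.3 acknowledges the difference: "Due to the difference in color between the active and control treatments, which are in opaque tubes". Its response is to keep drug-accountability staff away from assessments and from discussing treatment with assessors.

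**What patients do.** Under Protocol 6.1.3 they press the ointment strip onto an index finger and apply it to both lower lids. Under 4.2.2 and 6.1.1 they first practise at baseline with a product that, like the vehicle, is white petrolatum alone.

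**What they rate.** Change in Total OSDI at month 3 is one of two primary endpoints and is completed by the patient (Protocol 8.1.1 and 14.2). SAP 7.5 allows it to be tested only if MGS is significantly higher on active.

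**The concern.** Section 6.3 is the protocol's section on bias control, and it claims a masking property that the product description does not support. Opaque tubes hide the colour until the ointment is dispensed, not afterwards. A patient on active goes from a white practice dose to an orange, faintly smelling ointment; a patient on vehicle sees no change. Some may draw the obvious inference.

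If they do, any difference in expectation between arms adds directly to the OSDI treatment difference. SPEED, VAS and the comfort questionnaire are exposed in the same way. The MGS gate controls type I error across the two primary tests, but it does not remove such a bias from the OSDI estimate. At stake is how a positive symptom result may be described. A report that follows 6.3 could present OSDI as rated by masked patients; one that follows SAP section 2 would not.

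**Working it through.** **Step 1: set the statements side by side.**

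| Place | Are patients presented as masked? |
|---|---|
| Protocol 6.3 | Yes, named |
| Table 1, second part | Yes, by implication |
| Table 1, first part | No, investigator only |
| Protocol 1.2, 4.1, Figure 1 title | No, investigator only |
| SAP section 2 | No, investigator only |

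All of this is current text, and the two descriptions cannot both stand.

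**Step 2: do the safeguards reach the patient?** There are three: identical opaque tubes (6.3), separation of dispensing and accountability staff from assessors (4.2.2, 6.3), and Table 1 footnote f on masked assessors. The last two bind staff. The first stops working once ointment is on the finger.

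**Step 3: reproduce the plan's figures.** Inputs are from Protocol 9.1: OSDI SDs 13.01 and 6.79, MGS SDs 3.35 and 9.48, two-sided 0.05. I used a two-sample t-test with unequal variances (Satterthwaite df, noncentral t).

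- OSDI, 11 per group: SE = √((13.01² + 6.79²)/11) = √(215.36/11) = 4.42; 15.9/4.42 = 3.59; power 0.919.
- MGS, 12 per group: SE = √((3.35² + 9.48²)/12) = √(101.09/12) = 2.90; 10.4/2.90 = 3.58; power 0.914.

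These are the smallest group sizes reaching 90%, so the stated 11 and 12 reproduce. The masking point disputes neither.

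**Step 4: OSDI taken alone, under an assumed bias.** Assume 15 per arm (about 30 randomized 1:1, all analysed), no true OSDI effect, and a shift favouring active of 0, 2, 4.5 or 6.9 points. The 4.5 is the plan's responder threshold, not a bias estimate. The 6.9 is the whole 0.5% minus vehicle OSDI difference from AZ201801 (-6.9 minus 0.0, Protocol 2.2), so it is a high case. SE = √(215.36/15) = 3.79; noncentrality = shift/3.79; pooled t-test, df 28, critical value 2.048.

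| Shift | Noncentrality | Significant, favouring active | Same, SD 13.86 in both arms |
|---|---|---|---|
| 0 | 0 | 2.5% | 2.5% |
| 2 | 0.53 | 7.4% | 5.7% |
| 4.5 | 1.19 | 20.8% | 13.5% |
| 6.9 | 1.82 | 42.0% | 26.0% |

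The last column takes 4.0 × √12 = 13.86, assuming the ±4.0 given for the 0.5% group in Protocol 2.2 is a standard error with 12 patients.

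**Step 5: add the MGS gate.** Simulation with 400,000 trials per scenario and the plan's unequal SDs; the gate is MGS significantly higher on active. The entries are the chance of passing the gate and then falsely favouring active on OSDI, for shifts of 0, 2, 4.5 and 6.9.

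| MGS difference | Gate passed | MGS and OSDI independent | Within-patient correlation -0.4 (assumed) |
|---|---|---|---|
| 10.4 (planned) | 97% | 2.6%, 7.4%, 20.6%, 41.2% | 2.6%, 7.6%, 20.9%, 41.7% |
| 0.4 (4.9 minus 4.5, Protocol 2.2) | 3.9% | 0.1%, 0.3%, 0.8%, 1.6% | 0.3%, 0.8%, 1.6%, 2.5% |
| 0 | 2.8% | 0.1%, 0.2%, 0.6%, 1.1% | 0.2%, 0.5%, 1.2%, 1.9% |

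Hand check at 0.4 under independence: 0.039 × 0.420 = 0.016.

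Steps 4 and 5 use slightly different variance models (noncentral t with a common SD, then simulation with unequal SDs), so tenths of a point should not be compared between them. With unequal SDs, the ungated rate at zero shift is 2.6% rather than 2.5%. The planned ANCOVA with baseline OSDI (SAP 9.2) is not modelled and would move the figures somewhat.

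**The case against.** The strongest reply is that the limitation is already declared. The synopsis, section 4.1 and the SAP all say investigator-masked, and the SAP nowhere says patients are masked. Protocol 4.3 describes AZ201801 as double-masked, and SAP section 13 already identifies other wording left over from that study, so the stray text may simply be carry-over. That is plausible, though unproven, and it makes this largely a reconciliation of wording. It does not dispose of the point, because the section on bias control says the opposite of the label.

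The second reply is that each patient receives one assigned product, whereas accountability staff handle both, so the staff precaution does not show that patients can tell. This stands. A reader might infer that patients are effectively unmasked, or that the OSDI result would be invalid. The documents support neither. Nothing supplied says patients are told which colour is active, the consent text was removed before review, and the Dosing Instruction Sheet was not supplied. Being masked to assignment may also mean only that patients are not told it.

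Third, every bias size is assumed, and the large percentages require success on MGS. This also stands. A reader might take 42% as the trial's false-positive rate for OSDI; it is the rate at one high assumed shift once OSDI is being tested.

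A reader might also infer that masked MGS scoring is compromised because patients could describe the ointment to assessors. The documents give no indication of how likely that is.

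**Conclusion.** The contradiction is certain: 6.3 and one Table 1 heading say one thing, and every design statement says another. On the plan's own product description, patient masking is not assured for Total OSDI, SPEED, VAS or tolerability. The degree of unmasking, and so the size of any bias, is unknown from the supplied text.

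The percentages are illustrations that rest on the assumed shifts, 15 analysed per arm and the plan's SDs: about 7% to 42% once OSDI is tested, but at most about 1.6% (2.5% with the assumed correlation) after the gate at the reported 0.5% MGS difference of 0.4. The concern therefore matters mainly if the drug succeeds on MGS but has no symptom effect. It affects what may be concluded about OSDI. It does not invalidate the trial or its sample size.

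**What to change.** - Reconcile Protocol 6.3 and the two Table 1 headings with Protocol 1.2, 4.1 and SAP section 2.
- Keep the rule that patients are not told their assignment, but state in 6.3 that patient masking is not assured because of colour and odour.
- State in the SAP and in the study report that OSDI, SPEED, VAS and tolerability were rated without assured patient masking.
- Optional: check whether the general patient instructions already ask patients not to discuss their study ointment with assessors. Any such sentence should be neutral, should not name colour or smell, and should not be repeated as a reminder at each visit. Otherwise it could cue patients that these features distinguish the arms.

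**Cost:** wording only, with no new product, analysis or design change. The downside is a less favourable description of the OSDI evidence. The wording changes correct what can be concluded; they do not themselves reduce any bias.
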